10.2 Outcome Analysis Plan

Demographic characteristics for each group will be presented descriptively in tabular form. The primary outcome pertains to comparing the proportion of patients in each group with headache recurrence. Because of the small sample size, we will use a Fisher's exact test to compare the two groups on the primary outcome. A two-sided p-value less than 0.05 will be considered statistically significant. The relative risk of headache recurrence, together with a 95% confidence interval, will be computed.

The secondary outcomes will be analyzed in the same fashion as the primary outcome. The proportion of migraine recurrence at 7 days, the proportion of patients with return ED visits and the proportion of patients who achieve persistent pain freedom at 48 hours are all binary outcomes where the interest lies in comparing proportions between the two groups. The patient satisfaction outcome is an ordinal categorical variable with five possible responses graded on a Likert scale (see Appendix C). We will dichotomize this variable into two possible outcomes: 1) satisfied (coded as 1), where the sum of the frequencies for 'very satisfied' and

'satisfied' will be added together, 2) not satisfied (coded as 0), where the sum of the frequencies for 'neutral', 'unsatisfied' and 'very unsatisfied' will be added. Again, due to the small sample size, we will use a Fisher's exact test to compare the proportions between the groups for each secondary outcome.

Adverse events will be presented descriptively in tabular form, with the frequency and percentage of each adverse event listed by the corresponding group.

11. Safety and Adverse Events

11.1 Safety Assessments

As is described above, few adverse events are anticipated with single use of oral dexamethasone. The following are potential adverse events that could occur from single use of dexamethasone, as has been reported in the adult migraine literature as well as the pediatric literature where oral dexamethasone was used as a one time dose for other indications:

- Abdominal pain: In one pediatric study on single use oral dexamethasone in the pediatric population, 3.5% of patients reported abdominal pain. Should a patient experience significant abdominal pain after the administration of dexamethasone, the treating physician will administer analgesics at his or her discretion.
- Anaphylaxis/hypersensitivity reaction: Hypersensitivity reactions and anaphylaxis are listed as possible adverse drug reactions in the product monograph. In one of the adult intravenous dexamethasone studies, acute medication reactions occurred in less than 10% of the patients(24), and in one study a patient reported a rash(29). As per the product monograph, patients with anaphylaxis to dexamethasone will be managed in the ED with close monitoring of vital signs, airway support where required, appropriate doses of epinephrine and aminophylline if needed. Patients with hypersensitivity reactions will be closely monitored in the ED until the treating physician deems that discharge is safe. Treatment for hypersensitivity reactions will depend on the nature and severity of the reaction and will be administered at the discretion of the treating physician.
- Aseptic necrosis of the femoral and/or humeral head: Limited case reports have identified the possibility of aseptic necrosis of the femoral and/or humeral head following single doses of corticosteroids(46,47). Although this adverse event is exceedingly rare with single doses of corticosteroids, any patient reporting hip or shoulder pain in the ED will have anteroposterior and frog-leg radiographs of the hip(63) and/or shoulder radiographs to screen for aseptic necrosis of the affected joint. Should the radiographs not

reveal evidence of aseptic necrosis, an MRI will be pursued (63). Patients reporting the new onset of shoulder or hip pain during telephone follow-up will be instructed to return to the ED for an assessment. Patients with evidence of avascular necrosis will be urgently referred to Orthopedics for management.

- Blood pressure increase: Although blood pressure increase has been reported in one study on single use oral dexamethasone in the pediatric population, this increase did not require treatment and was clinically insignificant, with an average change in systolic blood pressure from 96.1mmHg ± 8.8mmHg to 99.5mmHg ± 14.8mmHg(45). We therefore do not anticipate that changes in blood pressure will constitute clinically significant events in our proposed study.
- Blurred vision: One adult patient reported blurred vision following a one time dose of oral dexamethasone in one of the randomized controlled trials(27). Although we do not anticipate that this will occur in our population, if a patient reports blurred vision while in the ED, the treating physician will reassess the patient and determine a plan of action. Should a patient report blurred vision during telephone follow-up, that patient will be instructed to return to the ED for an assessment.
- Diarrhea: Amongst the studies on single use oral dexamethasone reviewed, only one adult patient reported diarrhea in this context(27). If significant diarrhea occurs amongst one of the study patients, instructions will be given to the patient to return to the ED for an assessment.
- Drowsiness: In two of the adult intravenous dexamethasone studies, drowsiness was reported in under 25% of participants(24,25). Should a patient report drowsiness persisting beyond 24 hours, they will be instructed to discuss the symptom with their primary care provider or to return to the ED if the drowsiness is impairing or severe.
- Facial flushing: One adult patient given a single oral dose of dexamethasone
 to prevent migraine recurrence reported facial flushing(27). Although this
 will be recorded as an adverse event, it is a transient phenomenon that is not
 associated with any harm to the patient and does not require specific
 treatment.
- Hiccups: In one adult study of intravenous dexamethasone, hiccups were reported in one participant(20). This is expected to be a self-limited symptom. If hiccups persist or are disruptive to the participant, they will be asked to follow-up with their primary care provider.

- Muscle cramps: In one of the adult studies on intravenous dexamethasone in adults, one participant reported muscle cramps(21). Because muscle cramps may indicate an underlying electrolyte imbalance which is an adverse drug reaction reported in the product monograph, participants experiencing muscle cramps persisting beyond 7 days of discharge or which are continuous for more than 24 hours will be asked to return to the ED for an assessment.
- Nausea: Nausea does not appear to be a common side effect with single use oral dexamethasone, as it was reported by one adult in the studies reviewed. Should nausea occur in the ED setting, the treating physician will discuss treatment options with the patient. Should nausea occur after discharge and be reported in the telephone follow-ups, the patient will be instructed to return to the ED if symptoms are not responding to therapies at home.
- Pneumonia: In two of the pediatric studies, one where dexamethasone was given for croup(44) and the other where it was given for bronchiolitis(42), pneumonia was reported in less than 1% of patients. Although it is not anticipated that pneumonia will occur in our patient population, should any new respiratory symptoms or fever develop in the days following administration as reported on telephone follow-up, then patients will be instructed to return to the ED for a visit.
- Psychic derangements: Psychic derangements are listed as possible adverse drug reactions in the product monograph and have been reported in some of the studies reviewed. These include insomnia(20), mood changes (21,25), a feeling of restlessness(25), depression and euphoria. These derangements are expected to be self-limited if they occur. Participants reporting any of these symptoms will be instructed to discuss the symptom with their primary care provider if it persists for more than a week and is bothersome. In the case of severe psychic derangements (eg. severe depression with suicidal ideation), the participant will be instructed to return immediately to the ED.
- Swelling/weight gain: In one of the adult intravenous dexamethasone studies, less than 5% of participants reported swelling/weight gain(21). Weight gain is also listed in the product monograph in possible adverse drug reactions (see product monograph). Should a patient experience weight gain, they will be asked to follow-up with the primary care provider, unless the degree of weight gain is excessive in a short time frame indicating the need to have a more urgent assessment. Because significant weight gain may indicate an underlying electrolyte imbalance which is an adverse drug reaction reported in the product monograph, participants gaining more than 5% of their body weight within a week of discharge will be asked to return to the ED for an assessment.

- Unusual sensations in the extremities: Two adults have reported transient tingling sensations in the hands or feet in one of the adult studies or oral dexamethasone(27) and one adult reported a "hot sensation in the legs".. Should this type of symptom occur while a patient is in the ED, the treating physician will reassess the patient. Should a patient report this type of symptom at follow-up, they will be instructed to discuss the symptom with their primary care provider if it persists for more than 24 hours.
- Vomiting: In one of the pediatric studies, 5.5% of the patients receiving dexamethasone reported vomiting within 20 minutes of the administration of oral dexamethasone(42). Should this occur in our population, the treating physician will reassess the patient for management of vomiting and hydration status. Management changes will be at the discretion of the treating physician.

11.2 Methods and Timing of Safety Assessments and Follow-Up

As is described above, assessment of adverse events will occur during the ED visit at 2 hours post-intervention (or at the time of ED discharge if prior to 2 hours) and at discharge. During the 48 hour and 7 day electronic or telephone follow-ups, participants will again be asked if any adverse events have occurred. In the events where a participant indicates that an adverse event has occurred, they will be asked to describe those adverse events either in written form (for those completing electronic questionnaires) or verbally (for those completing telephone questionnaires). Participants completing electronic questionnaires and endorsing adverse events at follow-up will also be contacted over the telephone to clarify the nature of the adverse events. The Qualified Investigator or co-investigator will assess the potential relatedness of each AE to the investigational product during the trial.

All participants experiencing adverse events in the ED will be contacted over the telephone for follow-up (as opposed to being offered the option of electronic follow-up). Follow-up of adverse events occurring in the ED will also occur during the 48 hour and 7 day telephone follow-ups. In instances where the adverse event is first reported at the 7 day follow-up, an additional telephone follow-up 48 hours after the 7 day follow-up will be scheduled.

Although general follow-up timeframes are described above, extended follow-up will occur as required when the event does not resolve or stabilize within the above timeframes and the frequency, nature and timing of the extended follow-up will be determined by the Qualified Investigator. In addition, the Qualified Investigator may choose to schedule in-person follow-up in lieu of telephone follow-up when deemed necessary for participant safety.

11.3 Definitions Pertaining to Adverse Events

Adverse events (AEs) will be reported from the time the informed consent is obtained until the subject completes the last study procedure.

We will define AEs in accordance with the definitions set out by the International Conference on Harmonization (ICH E2A topic) and the CHEO REB SOP #REB-005:

Adverse event: Any symptom, sign, illness or experience that develops or worsens in severity during the course of the study. Intercurrent illnesses or injuries will be regarded as adverse events. Abnormal results of diagnostic procedures are considered to be adverse events if the abnormality:

- results in study withdrawal
- is associated with a serious adverse event
- is associated with clinical signs or symptoms
- leads to additional treatment or to further diagnostic tests
- is considered by the investigator to be of clinical significance

Adverse drug reaction: Any response to a drug, biologic, or natural health product which is noxious and unintended, which occurs at doses normally used or tested for the diagnosis, treatment or prevention of a disease or the modification of an organic function. A reaction, as opposed to an adverse event, is characterized by the fact that a causal relationship between the product and the occurrence is suspected (i.e. judged to be at least a reasonably possibility).

Important medical events are those that may not be immediately life threatening, but are clearly of major clinical significance. They may jeopardize the subject, and may require intervention to prevent one of the other serious outcomes noted above. For example, drug overdose or abuse, a seizure that did not result in in-patient hospitalization, or intensive treatment of bronchospasm in an emergency department would typically be considered serious.

Unexpected adverse drug reaction: An adverse reaction, the nature or severity of which is not consistent with the applicable product information (e.g. the Investigator's Brochure for an unapproved investigational product or package insert/summary of product characteristics for an approved product).

Unanticipated problem: Any incident, experience, or that meets **all** of the following criteria:

 Unexpected (in terms of nature, severity, or frequency) given (a) the research procedures that are described in the protocol-related documents, such as the REB-approved research protocol and informed consent document, or the

- Investigator Brochure; and (b) the characteristics of the research participant population being studied; and
- Related or possibly related to participation in the research (possibly related means there is a reasonable possibility that the incident, experience, or outcome may have been caused by the [investigational product(s)] or procedures involved in the research); and
- Suggests that the research places research participants or others at a greater risk of harm (including physical, psychological, economic, or social harm) than was previously known or recognized.

Serious adverse event: Adverse events will be classified as serious or non-serious. A serious adverse event is defined as any AE that is:

- fatal
- life-threatening
- requires or prolongs hospital stay
- results in persistent or significant disability or incapacity
- a congenital anomaly or birth defect
- an important medical event

The **severity** of an adverse event will be determined by the investigator, who should use the following definitions when assessing the intensity of an adverse event:

- 1. MILD: Participant is aware of symptoms or has minor findings but tolerates them well and no or minimal intervention required
- 2. MODERATE: Participant experiences enough symptoms or findings to require intervention
- 3. SEVERE: Participant experiences symptoms or findings that require significant intervention

An event will be qualified as **unexpected** when the specificity or severity of the event is not consistent with the package inserts or investigational brochure for the drugs under study.

Causality will be determined by the following question, where an affirmative answer designates the event as a suspected adverse reaction: Is there a reasonable possibility that the drug caused the event? "Reasonable possibility" means there is evidence to suggest a causal relationship between the drug and the specific adverse event being assessed.

In relation to the **identification of adverse events**, some participants in this study will have pre-existing medical conditions and those pre-existing conditions will not be considered as adverse events. New events that occur or the worsening in frequency or intensity of pre-existing conditions will be reported as adverse events (Schedule of Events). All reportable events as defined above, determined to be an AE based on physical examination, laboratory findings, or other means will be

recorded in the source documents and entered in the CRF. Each event will be recorded on an AE CRF starting after first dose of study drug has been delivered. The investigator will provide date of onset and resolution, severity, action(s) taken, changes in study drug dosing, causality to study drug, and outcome.

For **follow-up of AEs, a**ny safety event that is identified at the last assessment (or an early termination) will be recorded on the CRF with the status of the safety event noted. All serious suspected adverse reactions and serious adverse reactions will be followed until resolution or until the patient is medically stable.

11.4 Recording and Reporting of Adverse Events

All adverse events, adverse drug reactions and unanticipated problems will be recorded on the electronic adverse event form (see Appendix G), which will be stored in MICYRN.

Only adverse drug reactions that are **both** serious and unexpected are subject to expedited reporting to Health Canada. Expedited reporting of reactions which are serious but expected is not required. Expedited reporting is also inappropriate for serious events from clinical investigations that are considered unrelated to the study product, whether or not the event is expected.

During this trial, the sponsor (The Children's Hospital of Eastern Ontario) will inform Health Canada of any serious, unexpected adverse drug reaction that has occurred inside or outside Canada:

- a. where it is neither fatal nor life-threatening, within 15 days after becoming aware of the information:
- b. where it is fatal or life-threatening, immediately where possible and, in any event, within 7 days after becoming aware of the information; and
- c. within 8 days after having informed Health Canada of the ADR, submit as complete a report as possible which includes an assessment of the importance and implication of any findings.

Each ADR which is subject to expedited reporting will be reported individually in accordance with the data element(s) specified in the Health Canada / ICH Guidance Document *E2A: Clinical Safety Data Management: Definitions and Standards for Expedited Reporting*.

In situations when causality assessment and determination of expectedness is not straightforward, the report will be submitted in the expedited manner and the relevant issues will be outlined in a cover letter.

Final reports of fatal or life-threatening reactions will include an assessment of the importance and implication of the findings, including relevant previous experience with the same or similar drugs.

In addition to the above, if any additional situations arise, appropriate scientific and medical judgment will be applied to to determine if rapid communication to Health Canada is required. For example, information that might influence the risk-benefit assessment of a drug, or that would be sufficient to consider changes in drug administration, or in the overall conduct of a clinical trial, represent such situations where rapid communication to Health Canada will occur; including:

- a. for an "expected" serious ADR, an increase in the rate of occurrence which is judged clinically important;
- b. a significant hazard to the patient population, such as lack of efficacy with a drug used in treating a life-threatening disease; and
- c. a major safety finding from a newly completed animal study.

As per the ICH Good Clinical Practice Guidelines stipulations, the Children's Hospital of Eastern Ontario Research Ethics Boards will establish, document in writing and follow procedures for:

- Determining the frequency of continuing review as appropriate (including adverse drug reactions and adverse events) and
- Requiring that the **Investigator** should promptly report to the REB
 - Changes increasing the risk to subjects and/or affecting significantly the conduct of the trial;
 - All adverse drug reactions that are both serious and unexpected
 - New information may affect adversely, the safety of the subjects or the conduct of the trial.

In additions to the reporting to Health Canada as described above, all serious adverse events that occur at CHEO along with any adverse events that are both serious and unexpected, will be reported to the CHEO Research Ethics Board.

11.5 Treatment Discontinuation

Although this is a one time dose of oral dexamethasone, participants can decide to withdraw from the study at any time point. Participants withdrawing from the study will continue with the planned study follow-ups if they provide permission for ongoing follow-up.

11.6 Premature Study Discontinuation for Individual Participants

A participant will be permanently discontinued from the study when:

- Consent is withdrawn by the participant (ie. the participant requests to discontinue the trial)
- The investigator believe that ongoing participation in the trial will either pose a significant risk to the participant, invalidate the results of the study or involve a high risk of self-harm
- Loss to follow-up involving absence of all efficacy assessments and follow-up assessments for any reason

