Methodology	Randomized, double-blind, 2-arm parallel group trial				
Study Duration	6 months				
Study Center(s)	Single center: Children's Hospital of Eastern Ontario				
Objectives	To determine the feasibility of carrying out a multicenter randomized controlled trial to assess the efficacy of oral dexamethasone for preventing migraine recurrence in the pediatric ED through the implementation of a pilot randomized trial. The primary scientific objective will be to determine if oral dexamethasone is superior to placebo in preventing migraine recurrence within 48 hours of ED discharge amongst pediatric patients presenting to the ED with migraine.				
Number of Participants	20				
Diagnosis and Main Inclusion Criteria	Children and adolescents aged 8-18 years with migraine according to modified International Classification of Headache Disorders 3 rd edition (beta version) criteria				
Study Product, Dose, Route, Regimen	Dexamethasone 0.6mg/kg PO as a one time dose given in the emergency department (maximum of 15mg)				
Duration of administration	Single dose in the emergency department				
Reference therapy	Placebo				

Statistical Methodology Fisher's exact test will be used to compare the two groups on the primary outcome and on the secondary outcomes that involve proportions. Adverse events will be presented descriptively in tabular form, with the frequency and percentage of each adverse event listed by the corresponding group.		on the primary outcome and on the secondary outcomes that involve proportions. Adverse events will be presented descriptively in tabular form, with the frequency and percentage of each adverse event listed by the
---	--	--

4. Background Information and Clinical Data

Headache is very common in the pediatric population, with an estimated worldwide prevalence of 58.4% amongst children and adolescents(1). Given its prevalence, it is not surprising that it accounts for a significant proportion of pediatric emergency department (ED) visits: anywhere from 0.8-1.3% of all pediatric ED visits are due to headache(2–5). Although the majority of pediatric ED visits for headache are due to secondary causes, migraine accounts for between 5.4% and 28.7% of these visits(2–6).

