7.6 Study Intervention Administration and Efficacy Assessments

Once the baseline assessment is completed, the study intervention will be administered. Acute pain interventions will also be administered at the discretion of the treating physician. Pre-printed orders will be prepared by the research pharmacy in order to simplify study procedures and prevent errors. The pre-printed orders will be stored in study packages along with the consent forms and the informational brochures (see Appendix F). Three sets of study packages will be stored in the ED: one for each randomization stratum. The study intervention will be administered by the treating nurse.

A research assistant will assess pain 2 hours post-intervention and at the time of discharge, using the 4-point rating scale described above. Should the patient be discharged prior to the 2 hour post-intervention time point, the discharge pain assessment will replace the 2 hour post-intervention assessment. At the time of discharge, patient satisfaction will also be assessed by the research assistant, using a 5-point Likert scale where 5=very satisfied, 4=satisfied, 3=neutral, 2=unsatisfied, 1=very unsatisfied. In the event where a participant is discharged prior to having an efficacy assessment by the research assistant, an electronic questionnaire will be sent to the participant as a proxy for the inperson ED discharge assessment. If adverse events are reported on the electronic questionnaire, then the participant will be called to further assess the adverse event(s).

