7.9. Study Endpoints

7.8.1 Primary Outcome

The primary outcome will be headache recurrence 48 hours after discharge. Headache recurrence will be defined as: for patients who were pain-free at ED discharge (ie. pain intensity of 0), any return of head pain (ie. pain intensity of 1 or greater) will be coded as a recurrence, and for patients who had persistent head pain at discharge, an increase in head pain since ED discharge will be coded as recurrence as well (ie. an increase in their score on the 4-point scale as compared to their score at ED discharge). Therefore, the primary outcome will involve the comparison of the proportion of patients with headache recurrence in each group within 48 hours of ED discharge. Although formal statistics on reliability and validity are unavailable, assessment of the primary outcome, as described above, is congruent with prior studies on the efficacy of dexamethasone for this indication in adults (24,29).

The rationale for using headache recurrence as the primary outcome is derived from evidence from adult studies that have established efficacy for dexamethasone in preventing migraine recurrence in the short-term(15–18), but found no apparent impact on acute pain relief in the ED setting(57). The rationale for measuring recurrence of headache at 48 hours is three-fold: 1) the International Headache Society guidelines for controlled trials of drugs in migraine(11) defines recurrence as "any headache pain from 2 to 48 hours after drug administration, regardless of its severity", 2) prior studies assessed the efficacy of steroids (including dexamethasone) in preventing migraine recurrence anywhere from 24 to 72 hours after treatment, with the 48 hour mark being used most commonly(20,22,24–26,29,58–60), 3) the half-life of dexamethasone in children and adolescents is somewhere between 2.33 and 9.54 hours(50), meaning that it is cleared from the body between 11.7 and 47.7

hours after ingestion (after 5 half-lives only 3.1% of the drug remains in the body).

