12.1 Data Collection

All data in the ED will be collected by the research assistants. Follow-up data will either be self-reported through electronic questionnaires for participants selecting this option, or will be captured over the telephone by the research assistants. The participants and research assistants will remain blinded to group assignment and will assess and report all outcomes. Data will be inputted directly into an electronic CRF on the MICYRN instance of the Research Electronic Data Capture (REDCaP)(56) application (see Appendix C).

REDCap is a secure, web-based application hosted by the Women's and Children's Health Research Institute's Clinical Research Informatics Core that is compliant with ICH Good Clinical Practice Guidelines section 5.5.3. REDCaP is designed for the purposes of capturing data for research studies. REDCap provides: 1) an intuitive interface for data entry (with data validation); 2) 128 bit encryption between the data entry client and the server (https); 3) audit trails for tracking data manipulation and export procedures; 4) automated export procedures for seamless data downloads to common statistical packages (SPSS, SAS, Stata, R); 5) procedures

for importing data from external sources; and 6) advanced features, such as branching logic and calculated fields.

The Maternal Infant Child Youth Research Network (MICYRN), a network of academic health centres, was founded in 2006 as a collaborative national initiative to build capacity for high quality clinical research in Canada. Recognizing the need to establish and support standards in clinical research MICYRN has adopted the REDCap application to provide a shared data capture platform. The application is installed in a secure data centre provided by the Faculty of Medicine and Dentistry at the University of Alberta. It is managed and supported by the Women and Children's Health Research Institute's Clinical Research Informatics Core. The application has been validated by MICYRN members and is operated according to established standard operating procedures.

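### Section 11.6 ends study participation on an undefined, non-safety judgement that the results would be invalidated; after the single dose this can only stop outcome collection

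*Combined protocol and SAP*

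**What the plan says.** Section 11.6 opens with a mandatory formula, "A participant will be permanently discontinued from the study when", followed by three bullets: consent is withdrawn, the investigator makes a judgement, or the participant is lost to follow-up. The investigator bullet begins "The investigator believe that ongoing participation in the trial will either pose a significant risk to the participant" and goes on to add "invalidate the results of the study or involve a high risk of self-harm". It therefore holds two safety grounds (significant risk and self-harm) with one ground about the validity of the results between them. The validity ground has no criteria, time limit, documentation requirement or independent confirmation.

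Section 11.5 deals with participants who decide to withdraw: "Participants withdrawing from the study will continue with the planned study follow-ups if they provide permission for ongoing follow-up". It does not mention participants whom the investigator discontinues.

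The synopsis gives the duration of administration as "Single dose in the emergency department". Section 7.6 sets the timing: "Once the baseline assessment is completed, the study intervention will be administered". Section 7.8.1 sets the endpoint: "The primary outcome will be headache recurrence 48 hours after discharge". Section 10.2 specifies Fisher's exact test and a relative risk, but no analysis population and no rule for missing outcomes. Section 9.4 expects some loss to follow-up and makes monitoring its rate a goal of the pilot.

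**The concern.** In a trial with continuing treatment, a discontinuation rule can stop the drug while follow-up goes on. Here the drug has been given in full before the participant leaves the ED. Discontinuation after dosing can then act only on the remaining assessments: pain and adverse events in the ED, the 48-hour and 7-day questionnaires, and possibly the chart review. For the validity ground there is no participant-safety reason for that loss.

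Two things the pilot sets out to learn are exposed. Section 5.1 lists estimates of the proportion with recurrence in each group, and section 9.4 lists the rate of loss to follow-up. Each discretionary removal costs one outcome out of about ten per arm. Unless it is reported separately, it also blurs the retention figure. The pilot is meant to inform a multicentre trial, so the clause could be carried forward into it.

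**Working it through.** There is no stated figure to reproduce. The sample size of 20 in section 10.1 rests on recruitment feasibility, with no power calculation or dropout allowance. The check has two parts.

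**1. What the rule can do, by timing**

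- *Between randomisation and dosing.* Section 11.6 gives no timing, so the ground could be used here. It would still act after randomisation.
- *After dosing, before the 48-hour contact.* No treatment remains (synopsis, section 7.6). Recurrence has not yet been recorded (sections 7.7 and 7.8.1), so ending participation forgoes the primary outcome.
- *After the 48-hour contact, before day 7.* The primary outcome is already recorded. Seven-day recurrence would be lost.
- *Return ED visits.* These come from chart review (section 7.8) and may survive discontinuation.

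Two other sections could have protected these outcomes. Section 11.5 does not, because it covers only participants who withdraw themselves. Section 10.2 does not, because it names no analysis set and no missing-data rule.

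**2. Scale of one removal (illustration only)**

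Assumptions: 10 per arm, from 20 patients at 1:1; hypothetical recurrence of 3/10 on dexamethasone and 4/10 on placebo. Difference = dexamethasone proportion minus placebo proportion; RR = ratio of the two.

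| Participant lost | Counts | Difference (points) | Shift (points) | RR |
|---|---|---|---|---|
| None | 3/10 v 4/10 | 30.0 − 40.0 = −10.0 | – | 0.75 |
| Placebo, recurrence | 3/10 v 3/9 | 30.0 − 33.3 = −3.3 | +6.7 | 0.90 |
| Placebo, no recurrence | 3/10 v 4/9 | 30.0 − 44.4 = −14.4 | −4.4 | 0.675 |
| Dexamethasone, recurrence | 2/9 v 4/10 | 22.2 − 40.0 = −17.8 | −7.8 | 0.56 |
| Dexamethasone, no recurrence | 3/9 v 4/10 | 33.3 − 40.0 = −6.7 | +3.3 | 0.83 |

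The absolute shift runs from 3.3 to 7.8 points, depending on who is lost.

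The significance test is a lesser matter. One removal can cross the 0.05 line (3/10 v 8/10 has p = 0.070; 2/9 v 8/10 has p = 0.023), but only from an observed difference of 50 points. For a true difference of about 10 points, the exact power of Fisher's test at 10 per arm is about 2%, over assumed rate pairs from 23% v 34% to 58% v 68%. The practical effect is on the estimated proportions and the retention figure.

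**The case against.** Much of the case on the other side stands, and it limits the point. Several stronger readings are tempting but not supported.

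- *That the clause strips data from the analysis.* A reader might infer this, but section 11.6 concerns ongoing participation and does not say that recorded data are deleted. What is at risk is outcomes not yet collected. The missing analysis set in section 10.2 is a separate gap that leaves the risk uncovered.
- *That sections 11.5 and 11.6 contradict each other on this ground.* They do not. Section 11.5 is silent on investigator discontinuation. The real tension is with the first bullet of 11.6, which permanently discontinues participants who withdraw consent, while 11.5 keeps them in follow-up with permission.
- *That the investigator could see a recurrence and then remove the participant.* Recurrence is normally learned when it is recorded, and section 12.1 says "The participants and research assistants will remain blinded to group assignment and will assess and report all outcomes". Later discontinuation does not undo the record. A narrow route remains through ED pain, an adverse event or an early return visit. Section 7.4 also lets investigators see allocation data if safety issues or adverse events occur.
- *That the clause invites removal by direction of effect.* The text speaks of invalidating the results, not of changing them, and nothing suggests that frequent use is expected.
- *That investigator removals count as loss to follow-up.* Section 11.6 gives loss to follow-up its own bullet, so the two can be reported apart. The plan does not say that they will be.

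It is also fair to say that the 3-to-8-point shift measures the small sample. Any single loss, for any reason, would move the estimate as much. The difference here is that this loss is avoidable.

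**Conclusion.** The point holds as a minor one. Section 11.6 contains a mandatory, undefined, non-safety ground for ending participation. In a single-dose trial its only effect after dosing is to forgo outcomes not yet recorded, and neither section 11.5 nor section 10.2 prevents that. Blinding and pharmacy-held allocation make systematic bias by arm less likely, so the documents do not support a claim that the comparison would be biased in a known direction. What they do show is a discretionary loss of data after randomisation that the pilot need not accept. Under the hypothetical 3/10 v 4/10, each such loss shifts the estimated difference by about 3 to 8 points. That range rests on assumed counts and 10 per arm; how often the ground would be used is unknown. The safety grounds in the same bullet are not in question.

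**What to change.** 1. In the second bullet of section 11.6, delete the ground about invalidating the study results. Leave the two safety grounds as they stand.
2. State in sections 11.5 and 11.6 that, apart from those existing safety grounds and withdrawal of consent for follow-up, every randomised participant completes the 48-hour and 7-day follow-up and the chart review. State in section 10.2 that all are analysed in the assigned arm.
3. Record eligibility errors and protocol deviations under section 11.7, which already classes those with a potential impact on data integrity as major, without stopping outcome collection.
4. Report any investigator discontinuation by arm, separately from loss to follow-up.
5. Reconcile the first bullet of section 11.6 with the continued follow-up, with permission, in section 11.5.

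The cost is one deleted phrase and a few added sentences. No patients, visits or budget are added.
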